Protocol and Statistical Analysis Plan

Study Title: A Web-based Problem-Solving Program for African American Patients with Type 2 Diabetes

PI: [name]

April 23, 2021

Clinicaltrials.gov #NCT03855449

University of Kansas Medical Center
RESEARCH PROTOCOL INVOLVING HUMAN SUBJECTS
TEMPLATE WITH GUIDANCE

Version date: 4

Principal Investigator: [name]

Study Title: A Web-based Problem-Solving Program for African American Patients with Type 2 Diabetes

Co- Investigator(s): [name], [name], [name]

I. Purpose, Background and Rationale

A. Aim and Hypotheses

Significant disparities by race/ethnicity exist in the prevalence of type 2 diabetes and its health outcomes. In the US, diabetes affects 13.2% of African Americans, compared to 7.6% of Whites. Behavioral factors, such as poor diet, low physical activity, general lack of good self-management skills and self-care knowledge are associated with poor glucose control among African Americans. African Americans are 77% more likely to develop diabetes and its associated health complications compared to non-Hispanic Whites. Thus, this higher disease burden and lower adherence to self-management among African Americans calls for innovative approaches to self-management training. Problem solving is a reliable tool for the behavior change necessary to improve self-management, and the American Association of Diabetes Educators identifies it as one of 7 core diabetes self-management behaviors. One approach to helping African Americans develop the skills to solving problems is Problem Solving Skills Training (PSST). This therapeutic skill-training technique is delivered face-to-face to help patients identify their problems, learn skills to solve them, and implement solutions for particular challenges or obstacles in their disease self-management. Hill-Briggs and colleagues adapted PSST into a curriculum titled Decision-Making Education for Choices in Diabetes Every Day (**DECIDE**), which has successfully helped African American populations improve self-management behaviors, adherence, problem-solving and CVD clinical outcomes (HbA1c, Blood pressure, LDL, HDL). The specific aim is to:

1. Test eDECIDE in a pilot 18-week RCT, measuring change in HbA1c (primary outcome) and the following secondary outcomes: blood pressure, cholesterol, problem-solving skills, diabetes and cardiovascular disease knowledge, nutrition, and diabetes self-care behaviors.

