Primary Hypothesis: Participants randomized to eDECIDE (intervention group) will have comparable improvement in HbA1c compared to those randomized to traditional DECIDE (control group) at the end of 18-weeks.

Secondary Hypothesis: Participants randomized to eDECIDE (intervention group) will have comparable improvement in problem-solving skills, diabetes self-management knowledge and behaviors, and clinical measures compared to traditional DECIDE (control group) at the end of 18-weeks.

B. Background and Significance

1. **Study Significance:** This web-based approach will allow for future studies (using mHealth mobile applications) that can examine best practices for which type of problem-solving skills training is most effective to improve diabetes health outcomes for individuals. Results will inform the development of interventions aimed at reducing complications from uncontrolled diabetes as well as interventions aimed at promoting problem-solving and self-management. Identifying how to make problem-solving interventions more accessible would strengthen current investigations into improving health outcomes among underserved populations. It is believed that the minimal risk involved in the proposed study is reasonable considering that it could lead to more effective ways to manage diabetes among vulnerable. Since participation in traditional diabetes self-management programs is low, delivering tailored problem-solving skills training could increase self-efficacy and adherence among *African Americans*, thus improving glycemic control and further reducing health complications.

We propose to design and test a web-based application of the DECIDE curriculum for African Americans with uncontrolled diabetes. According to a Pew Internet study, 62% of African Americans have home access to the Internet,²⁷ and a previous web-based intervention indicated 80% of urban African Americans living with diabetes were using computers.²⁸ This application is not only a feasible approach to skills training, but innovative and cost-effective, allowing more flexibility, control, and self-directed access to training than face-to-face group sessions do. This new modality to deliver problem-solving interventions has the potential to reach much more of the African American population by providing easier access to diabetes self-management education.

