- B. **Study Type and Design:** This study is a randomized controlled trial pilot that will occur over an 18-week period. Participants will be recruited from local community health clinics and screened for A1C over 7.0% and clinical health measures (based on medical chart review), readability, Internet access, and cognitive impairment. Participants will be randomized into either the traditional DECIDE group (control) or the *eDECIDE* group (intervention). Traditional DECIDE consists of the regular 18-week in-person group sessions led by the candidate, as facilitator. The *eDECIDE* group sessions will consist of the newly translated online method. To assess problem-solving, diabetes self-care behaviors, diabetes and CVD knowledge, and dietary habits, participants will be administered the validated instruments listed in Table 5 at baseline, post-intervention, then at 3-month follow-up. Once participants are screened and randomized, they will be enrolled in the web-based program or the traditionally based program and complete a total of 18 weekly sessions. For *eDECIDE*, participants will have access to the weekly curriculum through a password-protected, interactive website. Participants in the intervention group will be asked to input their HbA1c number on the *eDECIDE* website. They will also be asked to create a unique username and password to login and use the *eDECIDE* website. All stored data will be secure and encrypted. Website is in development. Participants will be prompted to complete their workbook pages and answer any problems about barriers for the week. After prompting, participants will have the opportunity to submit their

completed workbook homework to their personal health coach (PI: [name]). Homework and sessions will be delivered through an eLearning system accessible through the eDECIDE website. Participants retrieve feedback via the website when logging back into their account. The personal health coach will not deliver problem-solving content. All content is scripted on the website and eLearning portal. Each week for 18 weeks, participants are asked to log on at least once for a total of 1 hour to complete the bi-weekly problem-solving training for that week. The training would include completing workbook pages and submitting responses to the coach. Participants in both groups will receive \$75 in gift cards (\$15 at first session, \$20 at completion of the 18 weeks, then \$20 at 3-month follow-up).

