C. Sample size, statistical methods, and power calculation

The primary outcome of interest is HbA1c measurement in the traditional DECIDE (control) group and eDECIDE (intervention) group. A .5% change in HbA1c has been considered clinically meaningful. The standard deviation in both arms is assumed to be 1.3%.⁶¹ Based on 2 sample t-test, assuming type I error rate of 5%, and attrition rate of 20%, with 35 participants in each group, the study is powered at 80% to detect a change in HbA1c level of at least 1% between the 2 groups. Hill-Briggs' intervention was successful in detecting HbA1c change of at least 1% in a previous study. We will recruit 100 participants allowing for attrition to reach our goal of 70 for the pilot RCT. Block randomization with block size of 10 will be employed. Within each block 5 participants will be assigned at random to control and 5 to intervention group using computer derived labels.

For baseline characteristics of data, descriptive statistics will be reported as mean and standard deviation for continuous variables, and as count and percentage for categorical variables. Depending on the distribution of the continuous variables Wilcoxon rank sum test or t-test will be used to test for difference in continuous variables across the control and intervention group. Chi-Square test of independence will be used to assess the association between categorical variables and the two groups. The analysis will be based on "Intention-to-treat" principle. A 2-sided p-value of 0.05 will be used to assess statistical significance. Missing Data: If the proportion of missing data is small (5%), complete case analysis will be carried out. If the proportion is higher, then multiple imputations will be used to impute missing values.

The post-intervention HbA1c levels in the intervention group will be compared to the control group using linear regression model after adjusting for baseline HbA1c levels. Additionally, average percentage change in HbA1c level across the 2 groups will be computed and compared using 2 sample t-test or Wilcoxon rank sum test (depending on the distribution of data).

The secondary outcomes of interest are additional clinical measures (blood pressure, LDL, HDL), dietary habits, diabetes self-management behaviors, Diabetes and CVD knowledge, and problem-solving skills for health-related problems as assessed by instruments listed in Table 5.

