- A. The post-intervention HbA1c levels in the intervention group will be compared to the control group using linear regression model after adjusting for baseline HbA1c levels. Additionally, average percentage change in HbA1c level across the 2 groups will be computed and compared using 2 sample t-test or Wilcoxon rank sum test (depending on the distribution of data).
- B. **Outcome:** The post-intervention HbA1c levels in the intervention group will be compared to the control group using linear regression model after adjusting for baseline HbA1c levels. Additionally average percentage change in HbA1c level across the 2 groups will be computed and compared using 2 sample t-test or Wilcoxon rank sum test (depending on the distribution of data). The secondary outcomes of interest are additional clinical measures (blood pressure, LDL, HDL), dietary habits, diabetes self-management behaviors, Diabetes and CVD knowledge, and problem-solving skills for health-related problems as assessed by instruments listed in Table 5.
- C. **Study results to participants:** We will make available any published study results. Our study team will also make available any community presentations to allow participants to learn about the final findings of the study and next steps.
- D. **Publication Plan:** We will publish study results to peer-reviewed journals: preliminary findings and a protocol paper. All identifying information will be removed before publication.

VI. Bibliography / References / Literature Cited: see attachment

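### One secondary hypothesis spans about seven outcomes under a general two-sided 0.05 rule with no order, multiplicity control or exploratory label; applied to each outcome, the rule gives a false difference somewhere with probability about 15% to 37%

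*Combined protocol and SAP*

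**What the plan says.** Section I.A names HbA1c as the single primary outcome. It then gives one secondary hypothesis for everything else: the eDECIDE arm "will have comparable improvement in problem-solving skills, diabetes self-management knowledge and behaviors, and clinical measures compared to traditional DECIDE", at the end of the 18 weeks.

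Sections II.C and V.B list what that hypothesis covers: "The secondary outcomes of interest are additional clinical measures (blood pressure, LDL, HDL), dietary habits, diabetes self-management behaviors, Diabetes and CVD knowledge", and then "problem-solving skills for health-related problems as assessed by instruments listed in Table 5". The list is not ranked.

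Sections II.C and V.3 each give the same threshold: "A 2-sided p-value of 0.05 will be used to assess statistical significance". Neither limits it to the primary outcome. The two HbA1c analyses (regression adjusted for baseline, and a comparison of percentage change) are written for HbA1c only, and no test is named for any secondary outcome.

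No section gives a testing order, a split of alpha, a condition on the primary result or an exploratory label. None says how mixed results across the outcomes would settle the single hypothesis. On the trial's status, section II.B says: "This study is a randomized controlled trial pilot that will occur over an 18-week period".

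**The concern.** A threshold of 0.05 controls the error of one test. When it is used on each of several outcomes, the chance that at least one crosses it by luck rises with the number of outcomes. Here the number is at least seven by a plain reading of the list, and the threshold is the only decision rule in the plan.

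Two consequences follow. First, if the arms really are alike, a chance difference on one outcome would count against the sponsor's own hypothesis of comparability, or would be reported as eDECIDE being better or worse on that outcome. Second, because no order is fixed in advance and section II.C.1 says the study is unblinded, whichever outcome crosses the line can be put forward once results are known. Section V.D plans peer-reviewed publication, so such a result would be read outside the study team.

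**Working it through.** **The plan's own figure.** The documents state no error rate for the secondary family. The figure they do state, 35 per arm for 80% power, concerns HbA1c only, and it reproduces:

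- Inputs (II.C): difference 1%, SD 1.3%, two-sided alpha 5%, attrition 20%.
- Normal approximation: n = 2 × (1.960 + 0.842)² × 1.3² / 1² = 26.5, so 27 per arm.
- Exact two-sample t-test: 27.5, so 28 per arm (power 80.7%).
- Attrition: 28 / 0.8 = 35 per arm.

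That calculation spends the whole 5% on one HbA1c comparison and makes no allowance for secondary tests.

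**Counting the secondary outcomes.** The list in II.C and V.B gives blood pressure, LDL, HDL, diet, self-management behaviour, knowledge and problem-solving: 7. Counting systolic and diastolic pressure separately adds one, and counting diabetes and CVD knowledge separately adds another: 9. Both splits are assumptions. The count is a reading of the list, because the instruments are deferred to Table 5, which is not in the available text.

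**If the tests are independent.** With m tests at 0.05 and no true difference, the chance of at least one p below 0.05 is 1 − 0.95^m:

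- m = 7: 1 − 0.95^7 = 30.2%
- m = 8: 1 − 0.95^8 = 33.7%
- m = 9: 1 − 0.95^9 = 37.0%

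**If the tests are correlated.** The documents give no correlation between outcomes, so a common correlation ρ is assumed and varied. With c = 1.96, and φ and Φ the standard normal density and distribution function:

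P = 1 − ∫ φ(u) × [Φ((c − √ρ·u)/√(1−ρ)) − Φ((−c − √ρ·u)/√(1−ρ))]^m du

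| ρ (assumed) | m = 7 | m = 8 | m = 9 |
|---|---|---|---|
| 0 | 30.17% | 33.66% | 36.98% |
| 0.3 | 27.15% | 29.97% | 32.63% |
| 0.5 | 22.96% | 25.01% | 26.92% |
| 0.8 | 14.86% | 15.75% | 16.55% |

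Simulated two-sample t-tests with 35 per arm agree. For m = 7 and m = 9 they give 30.2% and 37.0% at ρ = 0, 26.7% and 32.7% at 0.3, and 23.3% and 27.1% at 0.5.

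Against the nominal 5%, the range is 14.86 / 5 = 3.0 times to 36.98 / 5 = 7.4 times. The expected number of false differences does not depend on ρ: 7 × 0.05 = 0.35 to 9 × 0.05 = 0.45.

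**Three-month visit.** The secondary hypothesis is limited to 18 weeks, so the figures above are the relevant ones. The outcomes are also collected at 3 months, and nothing says whether they will be tested then. If they were, 14 to 18 tests would give 35% to 40% at ρ = 0.5. Under full independence the figure is 51% to 60%, which is an upper illustration because repeated measures are correlated.

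**The case against.** **No secondary test is written.** The threshold closes a paragraph that opens with baseline characteristics, and the secondary outcomes are only listed as being of interest. A reader might infer that the plan prescribes a 0.05 test for each outcome; it does not say so. This stands as a limit on the wording. But the same paragraph carries the intention-to-treat and missing-data rules, so it is not confined to baseline comparisons, and the plan offers no other rule for deciding the secondary hypothesis.

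**The hypothesis is comparability.** A chance significant result would count against the sponsor's hypothesis, not for it. If the hypothesis means comparability on every outcome, shown against margins, all outcomes must succeed and no alpha split is needed. This stands in part: the figures here do not measure a false claim of comparability. The opposite risk, that non-significance is taken as comparability when no margin is stated, is a separate matter that they say nothing about. But the plan has neither margins nor an all-outcomes rule. What it has is a threshold for differences, and applying that to several outcomes produces false contradictions at the rates shown.

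**It is a pilot.** The trial has one primary outcome and a feasibility goal, and these are already called secondary outcomes. That lowers the severity. It does not close the gap, because the plan states a formal secondary hypothesis, sets a threshold without exception, and in section II.D speaks of determining efficacy.

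**A gated key secondary.** A reader might want to promote one outcome, such as the problem-solving score, and test it only if the primary objective is met. The documents do not support this. They rank no secondary outcome, and the primary hypothesis is itself comparability with no margin, so there is no defined point at which it is met.

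**Conclusion.** The point holds. About seven outcomes sit under one hypothesis with a general two-sided 0.05 threshold and no order, multiplicity control or exploratory label. If the threshold is applied to each at 18 weeks and the arms do not differ, the chance of at least one false difference is about 23% to 27% at an assumed correlation of 0.5, within a range of about 15% to 37%.

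This rests on three assumptions: that the general threshold is applied to every secondary outcome, that there are seven to nine of them, and a common correlation that the documents do not supply.

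Two stronger readings are not supported. A reader might infer that a chance finding is to be expected; at roughly one in four, and below one half even under independence, it is not. A reader might also infer that the primary result is compromised; the HbA1c test is unaffected by the number of secondary outcomes. The plan should be changed on this point, but it does not put the trial's main comparison in doubt.

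**What to change.** In sections II.C and V.3, limit the two-sided 0.05 rule to the primary comparison, the baseline-adjusted HbA1c regression at 18 weeks. Then add, for example:

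*All secondary outcomes, at 18 weeks and at 3 months, are exploratory. Differences between arms will be reported with 95% confidence intervals, not adjusted for multiplicity, and no claim of statistical significance will be based on them.*

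In section I.A, reword the secondary hypothesis as an exploratory objective.

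Intervals also suit a question about comparability better than unadjusted p-values, because they show how large a difference the data leave open. The change takes a few sentences and adds no participants, visits or data. Its one small cost is that secondary outcomes can no longer be reported as significant findings.

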1. Inclusion criteria: Potential participants will be initially screened based on clinic (KU Internal Medicine Clinic) databases. They will be included if they have an HbA1c of > 7%, absence of significant comorbidities that limit adherence to self-management protocol, or expected to limit lifespan to < 3 years (chest pain, amputation, cancer diagnosis) based on medical chart audit review, are deemed suitable by clinicians, are African American, and are at least 21 years and older. The candidate will contact those who meet inclusion criteria to further undergo a telephone eligibility screen. The screen will ascertain eligibility based on no current participation in a self-management program and daily access to the Internet (in a home or private location).
2. Exclusion criteria: During the baseline visit, potential participants will then be screened for exclusion criteria: visual and cognitive impairment,⁵¹⁻⁵² inability to give informed consent, and unable to complete baseline assessment (clinical measures, study questionnaires, venipuncture).
3. Withdrawal/Termination criteria: Subject's participation will be terminated if requested by the subject. Subject's will need to continue to meet eligibility requirements to remain in the study (i.e. Internet access, etc.) to remain in the study.
4. A study subject can't participant in another study that is related to diabetes self-management as this may compromise out study outcomes.

E. Specific methods and techniques used throughout the study

1. **Laboratory tests:** Our study will collect and possibly perform blood draws (approximately 2 tablespoons)- to measure HbA1c and Cholesterol level. This blood draw would be collected at baseline, post-intervention (18 weeks) and again at 3-month follow-up. The laboratory test would be conducted either by the participating clinic or a contracted laboratory for participants to visit.

Behavioral questionnaires: Health-problem-solving survey, Diabetes self-care survey,

patient-provider communication survey

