2. We will always use a study id to identify a participant other than the raw database which will be kept in a secure REDCap database.
3. The Study team (PI, Research Assistant & Statistician) will have access to REDCap database with linked study IDs & participants full name.
4. linked by study ID in REDCap Secure Database.
5. REDCap Database, which is a secure password, protected program. Only study team members with access will be able to view the REDCap database.
6. study will test a website that will involve participants creating a username and password
7. Data will not be sent outside of KUMC

B. Sample / Specimen Collection: No samples will be collected at sites. Any laboratory collections will be done through a contracted provider or review of medical chart audit.

C. Tissue Banking Considerations: This is not relevant to this study. No tissue banking will take place.

D. Procedures to protect subject confidentiality: This study will use a secure website, hosted on KUMC server. Any and all data that must be transmitted will be encrypted and secure. No personal health information will be stored on

the website other than the participants chosen username and password. Website is underdevelopment and will be built to meet HIPPA qualifications.

E. Quality Assurance / Monitoring

1. Data will be kept in REDCap and maintained in this database to ensure data collection goals are met and subjects are monitored
2. No plans for 3rd party monitoring

V. Data Analysis and Reporting Stop Here

3. Statistical and Data Analysis:

For baseline characteristics of data, descriptive statistics will be reported as mean and standard deviation for continuous variables; and as count and percentage for categorical variables. Depending on the distribution of the continuous variables Wilcoxon rank sum test or t-test will be used to test for difference in continuous variables across the control and intervention group. Chi-Square test of independence will be used to assess the association between categorical variables and the two groups. The analysis will be based on “Intention-to-treat” principle. A 2-sided p-value of 0.05 will be used to assess statistical significance. Missing Data: If the proportion of missing data is small (5%), complete case analysis will be carried out. If the proportion is higher, then multiple imputations will be used to impute missing values.

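### The rule that participants must keep Internet access to remain in the study loses obtainable HbA1c outcomes after randomisation, contrary to the stated intention-to-treat principle

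*Combined protocol and SAP*

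**What the plan says.** Entry requires "daily access to the Internet (in a home or private location"), in both arms (II.D.1). The withdrawal section (II.D.3) turns this into a continuing condition: subjects "will need to continue to meet eligibility requirements to remain in the study (i.e. Internet access, etc".). The rule is not limited to one arm, and it concerns staying in the study, not only staying in the sessions.

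The HbA1c schedule in II.E.1 reads: "This blood draw would be collected at baseline, post-intervention (18 weeks) and again at 3-month follow-up". The test is done at a clinic or contracted laboratory. The timeline (II.E.5) lists the questionnaires as virtual at every visit.

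eDECIDE is delivered through a website. Control is described as in-person group sessions (II.B and II.E.2) or as self-directed paper (II.E.5). Neither form of control is delivered over the web.

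The analysis is to be "based on 'Intention-to-treat' principle" (II.C, repeated in V.3). Complete cases are used if about 5% or less is missing. Beyond that, "If the proportion is higher, then multiple imputations will be used to impute missing values". No imputation model or sensitivity analysis is given.

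**The concern.** Under intention-to-treat, every randomised participant is analysed in the assigned arm, which requires outcomes on all of them as far as they can be obtained. II.D.3 instead removes people for something that happens after randomisation. No section says that their later draws are still taken.

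The loss does not mean the same thing in the two arms. Losing access is one way in which web delivery fails, so a removed eDECIDE participant is likely to be one whose training was cut short. A removed control participant could have gone on receiving the sessions. Applying the rule equally to both arms therefore does not cancel its effect.

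The direction matters because the primary hypothesis (I.A) is that eDECIDE participants "will have comparable improvement in HbA1c compared to those randomized to traditional DECIDE". Removing those for whom web delivery failed moves the estimate towards that result. Once the blood has not been drawn, no analysis can recover the measured value.

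**Working it through.** **The plan's own figure.** II.C assumes SD 1.3, a difference of 1 HbA1c point, two-sided 5%, 80% power and an "attrition rate of 20" per cent. A two-sample t-test with standardised difference 1/1.3 needs 27.5, so 28 evaluable per arm (power 80.7%). Then 28/(1 - 0.20) = 35 per arm, as stated. The 20% allowance covers attrition from all causes.

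**Inputs for the bias.** None of these is in the documents; all are assumed.
- p, the share losing access during the 18 weeks: 5% to 20%.
- d, the HbA1c benefit lost by an eDECIDE participant who loses access: 0.5 to 0.75 points. The upper value is an assumed full fall of 0.75 in each arm.
- Lost access does not change the benefit of control sessions.
- Losing access is otherwise unrelated to HbA1c, and the arms would be equal if everyone kept access.

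**Formula.** Let m be the mean 18-week HbA1c with access kept.
- All outcomes collected: the eDECIDE mean is (1 - p)m + p(m + d) = m + pd and the control mean is m, so the difference is pd.
- Removal and complete cases: m - m = 0.
- Removal and imputation from arm and baseline: the filled-in values come from retained participants in the same arm, so the difference is again 0.

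The hidden difference is therefore p × d.

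| p | d | p × d | share of 0.5 |
|---|---|---|---|
| 0.05 | 0.50 | 0.025 | 5% |
| 0.10 | 0.50 | 0.050 | 10% |
| 0.10 | 0.75 | 0.075 | 15% |
| 0.20 | 0.75 | 0.150 | 30% |

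The last column uses the 0.5% change that II.C calls clinically meaningful. It is a yardstick, not a margin.

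**Timing.** If access is lost at a uniformly random time and the benefit lost is proportional to the sessions missed, the mean of d halves. The range becomes 0.025/2 = 0.0125 to 0.150/2 = 0.075. At p = 0.10 it is 0.025 to 0.0375.

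**Arithmetic check.** A simulation of the baseline-adjusted regression used 400,000 per arm, SD 1.3, and assumed baseline mean 8.9, correlation 0.6 and fall 0.75. For p = 0.20 and d = 0.75 it gave a difference of 0.150 with all outcomes collected, 0.001 with complete cases and 0.000 with imputation from arm and baseline. This confirms the algebra; it is not evidence about the inputs.

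**The case against.** *The failures are not hidden.* Drop-outs are monitored and reported every 12 months (II.F.2), and website log-ons are reviewed (II.L.1). A reader might infer that the rule conceals eDECIDE delivery failures altogether. The documents do not support that: failures remain partly visible as counts, although II.F.2 does not promise counts by arm or reason. What is lost is narrower, namely the HbA1c and questionnaire results of those participants.

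*Internet access has a use in both arms.* The questionnaires are virtual, and both arms receive weekly email or text reminders (II.E.5). The rule thus has an operational reason, and assuming no effect of lost access in control is a simplification. This stands, but it does not explain forgoing a laboratory draw, and questionnaires can be given by telephone or on paper.

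*Multiple imputation is planned.* No model is specified, so one that uses log-ons is not excluded. It could soften the problem but could not replace a measured value, and at about 5% missing or less the plan uses complete cases.

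*The size is small and assumed.* This stands. The plan tests for a difference and sets no equivalence or non-inferiority margin, so the bias cannot be tied to a decision threshold. Nothing shows that it would change the trial's conclusion.

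**Conclusion.** The point holds as a conflict between a stated withdrawal rule and a stated analysis principle. Following II.D.3 loses obtainable primary outcomes for a post-randomisation reason that stops session delivery only in eDECIDE, and the resulting bias favours the hypothesis.

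Its size cannot be computed from the documents. Under the assumed inputs it is about 0.01 to 0.15 HbA1c points. The low end is more plausible: daily access is required at entry, 20% is the power calculation's allowance for attrition of every kind, and access lost part-way costs only part of the benefit.

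A reader might go further and infer that the rule could by itself produce a false finding of comparability. The figures do not support that. Severity is minor to moderate, and the main reason to act is that the remedy is cheap while the lost data cannot be recovered.

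**What to change.** In II.D.3, state that loss of Internet access after randomisation may stop the web sessions but does not remove the participant from the study. State also that the 18-week and 3-month HbA1c draws and questionnaires are collected on every randomised participant, with questionnaires by telephone or on paper where the virtual form cannot be used. The exceptions are withdrawal of consent and any case in which the protocol or the IRB bars study procedures.

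The cost is the amendment wording, a few more blood draws at visits already scheduled, and a few telephone or paper questionnaires. The stated sample size does not change.
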